5.6.2 Ixazomib

Adverse drug reactions such as thrombocytopenia, diarrhea, fatigue, nausea, vomiting, and rash have been associated with ixazomib treatment. Management guidelines regarding these events are outlined below. Further details of management of ixazomib AEs are described in Section 6 of the Ixazomib IB.

Prophylaxis against Risk of Infection

If lymphopenia is noted, patients may be at an increased risk of infection. In particular, lymphopenia can be associated with reactivation of herpes zoster and herpes simplex viruses. Antiviral therapy such

as acyclovir or valacyclovir will be initiated as clinically indicated. Other antivirals are also acceptable, as clinically indicated.

Nausea and/or Vomiting

Antiemetics: prefer that non-5-HT₃ serotonin receptor antagonists be used at the discretion of the investigator. The dose and regimen will be according to institutional guidelines. If 5-HT₃ serotonin receptor antagonists are required for nausea refractory to initial agents, then monitoring the QT interval is necessary with periodic EKGs.

Fluid deficits should be corrected before initiation of study drug and during treatment.

Diarrhea

Diarrhea should be managed according to clinical practice, including the administration of antidiarrheals once infectious causes are excluded. Fluid intake should be maintained to avoid dehydration. Fluid deficits should be corrected before initiation of treatment and during treatment. Prophylactic antidiarrheals are not generally recommended.

Erythematous Rash With or Without Pruritus

As with VELCADE, rash with or without pruritus has been reported with ixazomib, primarily at the higher doses tested and when given with agents for which rash is an overlapping toxicity. The rash may range from some erythematous areas, macular and/or small papular bumps that may or may not be pruritic over a few areas of the body to a more generalized eruption that is predominately on the trunk or extremities. Rash has been most commonly characterized as maculopapular or macular. To date, when it does occur, rash is most commonly reported within the first 3 cycles of therapy. The first incidence of rash events occurred early during treatment, and there was no evidence of increased frequency of rash with prolonged exposure. The rash is often transient, self-limiting (resolves without medical intervention), and is typically Grade 1 to 2 in severity.

Symptomatic measures such as oral or topical corticosteroids and/or antihistamines have been successfully used to manage rash and have been used prophylactically in subsequent cycles. The use of a topical, IV, or oral steroid (eg, prednisone ≤ 10 mg per day or equivalent) is permitted. Management of a Grade 3 rash may require IV antihistamines or corticosteroids. Administration of ixazomib (and/or other causative agents if given in combination) should be modified per protocol and re-initiated at a reduced dose level from where rash was noted.

In line with clinical practice, dermatology consult and biopsy of \geq Grade 3 rash or any SAE involving rash are recommended at the discretion of the investigator. Prophylactic measures should also be considered if a patient has previously developed a rash (eg, using a thick, alcohol-free emollient cream on dry areas of the body or oral or topical antihistamines). The rare risks of Stevens-Johnson syndrome, TEN, DRESS syndrome, and pemphigus vulgaris have been reported in oncology studies when ixazomib (or placebo) has been given in a multi-therapy regimen, with concomitant medications known to cause rash, and/or in the setting of confounding TEAEs. These severe, potentially life-threatening, or deadly conditions may involve rash with skin peeling and mouth sores and should be clinically managed according to standard medical practice. Study medications should be discontinued in the event of severe, potentially life-threatening rash.

Thrombocytopenia

Thrombocytopenia has been reported to date primarily at the higher doses tested. Blood counts should be monitored regularly as outlined in the protocol with additional testing obtained according to standard clinical practice. Thrombocytopenia may be severe but has been manageable with platelet transfusions according to standard clinical practice. Thrombocytopenia nadirs commonly recover without intervention by the beginning of the next scheduled cycle. Ixazomib administration should be modified as noted as per dose modification recommendations in Table 6.2 when thrombocytopenia occurs. Therapy can be reinitiated at a reduced level upon recovery of platelet counts. A rare risk is thrombotic thrombocytopenic purpura (TTP), a rare blood disorder where blood clots form in small blood vessels throughout the body characterized by thrombocytopenia, petechiae, fever, or possibly more serious signs and symptoms. TTP should be managed symptomatically according to standard medical practice.

Neutropenia

Neutropenia has been reported. Blood counts should be monitored regularly as outlined in the protocol with additional testing obtained according to standard clinical practice. Neutropenia may be severe but has been manageable with G-CSF according to standard clinical practice. Neutropenic nadirs commonly recover without intervention by the beginning of the next scheduled cycle or with a short delay in treatment. Ixazomib administration should be modified when neutropenia occurs, as noted in the dose modification recommendations in Table 6.2. Therapy can be reinitiated at a reduced level upon recovery of absolute neutrophil counts.

Fluid Deficits

Dehydration should be avoided because ixazomib may cause vomiting, diarrhea, and dehydration. Acute renal failure has been reported with ixazomib. Fluid deficits should be corrected before initiation of study drug and during treatment and as needed during therapy. Until further information is available, intake of NSAIDs while on this protocol should be avoided.

Hypotension

Symptomatic hypotension and orthostatic hypotension with or without syncope have been reported with ixazomib. Blood pressure should be closely monitored while the patient is on study treatment and fluid deficit should be corrected as needed, especially in the setting of concomitant symptoms such as nausea, vomiting, diarrhea, or anorexia. Patients taking medications and/or diuretics to manage their blood pressure (for either hypo- or hypertension) should be managed according to standard clinical practice, including considerations for dose adjustments of their concomitant medications during the course of the trial.

Posterior Reversible Encephalopathy Syndrome

Posterior reversible encephalopathy syndrome (PRES), which ultimately resolved, has been reported with ixazomib. PRES is characterized by headache, seizures and visual loss, as well as abrupt increase in blood pressure. Diagnosis may be confirmed by magnetic resonance imaging. If the syndrome is diagnosed or suspected, symptom-directed and medical treatment should be maintained until the condition is reversed by control of hypertension or other instigating factors. Prompt diagnosis and initiation of antihypertensive and anticonvulsant therapy are important to prevent irreversible end-organ damage.

Transverse Myelitis

Transverse myelitis has been reported with ixazomib. It is not known whether ixazomib causes transverse myelitis; however, the possibility that ixazomib may have contributed to transverse myelitis cannot be excluded. Transverse myelitis should be managed according to standard medical practice.

Progressive multifocal leukoencephalopathy

PML, which may be fatal, has occurred in less than 1% of oncology patients receiving ixazomib in combination with other cancer therapies. It is not known whether ixazomib causes PML; however, the possibility that ixazomib may have contributed to PML cannot be excluded. In the event of occurrence of PML, ixazomib should be discontinued and supportive care provided as needed.

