
 • Delay of > 2 weeks in the start of a subsequent cycle due inadequate recovery to goals outlined above. 	
 • Hold romidepsin and ixazomib until resolution as per criteria above • Obtain CBC with diff 2x/week until platelet count or ANC have reached goal outlined above

Toxicity	Action
	
 Upon recovery, reinitiate treatment at 1 dose level reduction as per section 6.3. The maximum delay before treatment may be discontinued is 21 days and at the discretion of the local PI.

 Grade 4 febrile neutropenia or thrombocytopenia 	
 Hold treatment Obtain CBC with diff 2x/week until platelet count or ANC have reached goal outlined above Upon recovery, reinitiate treatment at 1 dose level reduction as per section 6.3.

Non-Hematological Toxicity Dose Reductions Related to Study Drugs (except alopecia)

NCI CTCAE Grade	Romidepsin	Ixazomib
0-1	No change	No change
2-3	Hold until resolved to \leq Grade 1, then resume at same level	Hold until resolved to \leq Grade 1, then resume at same level with exceptions as outlined in table “Non-hematological Toxicity Dose Reductions specific to Ixazomib”
Second episode of grade 3 OR First episode 4 toxicity	Hold until resolved to \leq Grade 1, then resume at 1 dose level reduction as per section 6.3.	Hold until resolved to \leq Grade 1, then resume at 1 dose level reduction as per section 6.3.
Third episode of grade 3 OR Second episode 4 toxicity	Hold until resolved to \leq Grade 1, then resume at 1 dose level reduction as per section 6.3. If toxicity occurs at lowest dose level, then treatment should be discontinued	Hold until resolved to \leq Grade 1, then resume at 1 dose level reduction as per section 6.3 or discontinue based on local PI judgement If toxicity occurs at lowest dose level, then treatment should be discontinued

Non-hematological Toxicity Dose Reductions specific to Ixazomib:

Peripheral Neuropathy	

 New or worsening Grade 1 peripheral neuropathy with pain or Grade 2 	
 Hold study drug until resolution to Grade \leq 1 or baseline

 New or worsening Grade 2 peripheral neuropathy with pain or Grade 3 	
 Hold study drug until resolution to Grade \leq 1 or baseline Reduce study drug to next lower dose upon recovery

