
 New or worsening Grade 4 peripheral neuropathy 	
 Discontinue study drug
Rash	

 Grade 2 	
 Symptomatic recommendations outlined in Section 5.4

Dosage in Patients with Hepatic Impairment

Reduce the starting dose of ixazomib to 3 mg in patients with moderate (total bilirubin greater than 1.5-3 x ULN) or severe (total bilirubin greater than 3 x ULN) hepatic impairment.

Dosage in Patients with Renal Impairment

Reduce the starting dose of ixazomib to 3 mg in patients with severe renal impairment (creatinine clearance less than 30 mL/min) or end-stage renal disease (ESRD) requiring dialysis. Ixazomib is not dialyzable and therefore can be administered without regard to the timing of dialysis.

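### Section 5.6.2 and the Phase I tables in Section 6.2 give different instructions after life-threatening rash and after Grade 3 rash, and no text says which prevails

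*Combined protocol and SAP*

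**What the plan says.** Section 5.6.2, under erythematous rash, gives two dosing instructions.

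- After listing Stevens-Johnson syndrome (SJS), TEN, DRESS and pemphigus vulgaris as rare risks: "Study medications should be discontinued in the event of severe, potentially life-threatening rash". No CTCAE grade is attached.
- After the sentence "Management of a Grade 3 rash may require IV antihistamines or corticosteroids", it says that ixazomib, and/or another causative agent in the combination, is to be modified per protocol and "re-initiated at a reduced dose level from where rash was noted". This sentence names no grade either.

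Section 6.2 holds the Phase I dose-modification tables. The general non-hematologic table covers every related toxicity except alopecia, so it covers rash.

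- Grade 2-3 row: hold both drugs until Grade 1 or lower, then restart at the same level. The ixazomib column alone adds a qualifier: "resume at same level with exceptions as outlined in table", meaning the ixazomib-specific table.
- Row labelled "Second episode of grade 3 OR First episode 4 toxicity": hold both drugs until Grade 1 or lower, "then resume at 1 dose level reduction as per section 6.3".

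The ixazomib-specific table has one rash row, for Grade 2. Its whole content is "Symptomatic recommendations outlined in Section 5.4". Section 5.4 covers drug administration; the rash advice is in Section 5.6.2. The same table does stop drug for Grade 4 peripheral neuropathy.

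Section 6.4 refers toxicity-related discontinuation to Section 6.1, which defines DLT and MTD and has no rule for taking a patient off drug.

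**The concern.** An investigator deciding whether to restart after a serious rash finds two operative instructions that differ. The table in Section 6.2 is where a site would look for dosing actions. For thrombocytopenia and neutropenia, Section 5.6.2 itself sends the reader to Table 6.2. A site that applied the table literally could re-expose a patient whom Section 5.6.2 takes off drug. It could also restart after a first Grade 3 rash without the reduction that Section 5.6.2 asks for. Re-exposure is the rarer and more serious of these errors. What is at stake is patient safety and uniform dosing across sites. No statistical property of the design is involved.

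**Working it through.** No arithmetic bears on the conflict itself, so the check sets the rules side by side.

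| Event (related rash) | Section 5.6.2 | Section 6.2 general table | Section 6.2 ixazomib exceptions |
|---|---|---|---|
| Life-threatening, graded 4, first episode | Discontinue study medications | Hold, then resume both drugs one level down | No rash row; the exceptions qualifier is absent from this row |
| Life-threatening, graded 3, first episode | Discontinue study medications | Hold, then resume both drugs at the same level | No Grade 3 rash row |
| Other Grade 3, first episode | Restart at a reduced level (grade read from the preceding sentence) | Hold, then resume at the same level | No Grade 3 rash row |
| Other Grade 3, second episode | Restart at a reduced level | Hold, then resume one level down | Not needed; the two agree |

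**Can the words be reconciled?**

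1. *Discontinue as a temporary hold.* This does not work. The Section 6.2 tables use hold for an interruption and discontinue for a stop.
2. *Modified per protocol as deference to Section 6.2.* This works only in part. The same sentence goes on to require a reduced level, which Section 6.2 does not give after a first Grade 3 event.
3. *The restart sentence as ungraded.* If it covers all rash, it still disagrees with the Grade 2-3 row, so the mismatch does not depend on reading it as Grade 3.
4. *The exceptions table as the bridge.* It has no Grade 3 or Grade 4 rash row, and its one pointer leads to the wrong section.

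**Link to the DLT definition.** Rash is not among the exclusions in the non-hematologic row of Section 6.1. A related Grade 3 rash in cycle 1 is therefore a DLT, yet Section 6.2 lets that patient resume at the same level. The DLT is counted whatever dose the patient receives next, so the model input is the same under either rule.

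**What one level down means.** Planned dose per 28-day cycle, from Section 6.3 (dose x number of days):

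- Level 6: romidepsin 3 x 14 = 42 mg/m²; ixazomib 3 x 4 = 12 mg
- Level 5: romidepsin 2 x 14 = 28 mg/m²; ixazomib 3 x 4 = 12 mg
- Level 4: romidepsin 3 x 10 = 30 mg/m²; ixazomib 3 x 4 = 12 mg
- Level 3: romidepsin 3 x 10 = 30 mg/m²; ixazomib 3 x 3 = 9 mg

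The change in ixazomib is 0% from level 6 to 5, 0% from level 5 to 4, and (9 - 12)/12 = -25% from level 4 to 3. From level 5 to 4, planned romidepsin per cycle rises from 28 to 30 mg/m², although each infusion falls from 14 to 10. So a one-level reduction from level 6 or 5 leaves ixazomib at 4 mg on days 1, 8 and 15.

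**The case against.** The strongest reply is that Section 5.6.2 is the specific rule and Section 6.2 the generic default. The protocol treats PML in the same way: Section 5.6.2 stops ixazomib, and Section 6.2 has no PML row. On that reading, Section 5.6.2 holds event-specific stops that the table need not repeat, and re-treating SJS or TEN would mean ignoring an explicit instruction.

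Other safeguards point the same way. Treatment continues only until unacceptable toxicity (Section 5.1). The treating physician may stop therapy, and an interruption of 21 days or more can end it (Section 6.4). SAEs go to headquarters within 1 business day and to the sponsor-investigator for prompt review (Section 11.2.2). Phase I has weekly team meetings and DSMC oversight (Section 13).

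This stands as a reason to think re-treatment after life-threatening rash unlikely. It does not correct the table, and no text gives Section 5.6.2 precedence. It helps less with Grade 3 rash, where both texts allow a restart and differ only on the dose, so a site has no obvious signal that something is wrong.

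Three limits also stand. The Grade 3 reading comes from the preceding sentence. Section 6 of the Investigator's Brochure, cited for managing ixazomib events, was not available. The tables were read from PDF, so a lost rash row is possible, though nothing indicates one.

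A reader might infer that the protocol directs sites to re-treat life-threatening rash, or that the dose finding is compromised. The documents support neither. Section 5.6.2 says the opposite of the first, and the DLT definition, the MTD rule and the CR endpoint do not depend on which rash rule is followed.

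**Conclusion.** The inconsistency is real and lies in current, operative text, so it should be fixed. It has two limbs:

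- Life-threatening rash is stopped in Section 5.6.2 but can be re-treated under the Section 6.2 table.
- A first Grade 3 rash is restarted at a reduced level in Section 5.6.2 but at the same level in Section 6.2.

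The first limb is firm on the wording and unlikely to be acted on. The second rests on reading the restart sentence in context and is easier to act on by mistake.

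The scope is Phase I, planned at 18 to 36 patients, with fewer if the toxicity stop after the first six applies. Phase II dose modifications are still to be written. A reader might want a probability of harm, but the documents cannot supply one. They give no rate for severe rash in this combination, and say only that the named conditions are rare and that rash is typically Grade 1 to 2. Nor do they say how often a patient would recover, stay on study and be restarted against Section 5.6.2. No MTD, CR, power or error figure changes.

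**What to change.** In Section 6.2, add two rows that bind both the romidepsin and the ixazomib columns. Placed in the ixazomib-specific table as it now stands, they would not govern romidepsin.

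- (a) Severe, potentially life-threatening rash (e.g. SJS, TEN, DRESS, pemphigus vulgaris), any grade: discontinue study medications per Section 5.6.2; do not resume.
- (b) Grade 3 rash: hold to Grade 1 or lower, then resume one dose level down per Section 6.3.

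State that these rows override the general table, including its Grade 4 row. Change the rash pointer from Section 5.4 to 5.6.2, and the toxicity pointer in Section 6.4 from 6.1 to 6.2 and 5.6.2. Carry both rows into the Phase II rules when they are written.

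Two matters are for the sponsor-investigator. One is to confirm that the restart sentence in Section 5.6.2 is meant for Grade 3 rash. The other is whether a restart from level 6 or 5 should go further down, since one level leaves ixazomib at 4 mg. Going straight to level 3 would use an existing pairing, but row (b) would then have to say that it skips levels.

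The cost is a protocol amendment with two rows, one precedence sentence and two cross-references. It needs no new visits, data or patients.

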6. TOXICITIES AND DOSE DELAYS/DOSE MODIFICATIONS

The NCI Common Terminology Criteria for Adverse Events (CTCAE) v4 will be used to grade adverse events.

Subjects enrolled in this study will be evaluated clinically and with standard laboratory tests before and at regular intervals during their participation in this study as specified in Study Calendar & Evaluations.

Subjects will be evaluated for adverse events (all grades), serious adverse events, and adverse events requiring study drug interruption or discontinuation as specified in Study Calendar & Evaluations.

6.1 Dose limiting Toxicity (DLT) and Maximally Tolerated Dose (MTD)

Phase I: DLTs occurring during the 1st cycle of treatment with the combination of ixazomib and romidepsin will be used for dose-escalation decisions. The *true* MTD is defined as the largest dose at which no more than 25% of patients experience a DLT; the *estimated* MTD will be the dose level with a model-estimated rate of DLT closest to 25% (but not more than 33%).

Definition DLT: A DLT is defined as any of the following adverse events (AEs) that are possibly, probably, or definitely related to the combination of ixazomib and romidepsin that occurs during the 1st cycle (28 days). The NCI Common Terminology Criteria for Adverse Events (CTCAE), Version 4 will be used to assess toxicities.

Toxicity Category	Drug-Related Toxicity/Grade
Hematologic	Grade 4 Neutropenia for ≥ 14 days
	Febrile neutropenia: Grade 3 or 4 neutropenia with fever $> 38^{\circ}\text{C}$, both sustained over a 24-hour period
	Anemia, Grade 3 or 4
	Thrombocytopenia: Grade ≥ 4 lasting greater than 7 days or Grade ≥ 3 complicated by at least a Grade 2 hemorrhage
Non-Hematologic	Grade 3 or 4 toxicity (excluding alopecia, fatigue or anorexia lasting < 7 days, or Grade 3 nausea and/or vomiting that persists for < 2 days following appropriate supportive care). Nausea, vomiting, or diarrhea must persist at Grade 3 or 4 despite maximal medical therapy

Toxicity Category	Drug-Related Toxicity/Grade
Infection	Grade 3 or Grade 4
Any	Grade 5
Electrolyte abnormalities	Grade ≥ 3 electrolyte abnormalities that do not resolve to \leq Grade 2 or baseline within 7 days
Grade 4 leukopenia or lymphopenia will NOT be considered a DLT	

6.2 Dose Modifications

Dose modifications below are outlined for the Phase I portion of the trial. Further information on the Phase II dose modification will be determined after the MTD is established.

Treatment with romidepsin and ixazomib will use a cycle length of 28 days. Missed doses within a cycle will not be made up. For example, if drug is held on Day 8 and given the next week, the day of administration will be Day 15; Day 8 will be considered as missed. Once a dose of romidepsin or ixazomib is reduced, the dose may only be re-escalated after discussion with and approval by the sponsor investigator. If a delay occurs on day 1 of a cycle, then day 1 will be when the first dose of a cycle is given.

For a new cycle of treatment to begin or resumption of treatment within a cycle, the patient must meet the following criteria:

- ANC $\geq 1,000/\text{mm}^3$.
- Platelet count $\geq 75,000/\text{mm}^3$.
- Concurrent magnesium and potassium supplementation is allowed to maintain levels within a normal range.
- All other nonhematologic toxicity (except for alopecia) must have resolved to \leq Grade 1 or to the patient's baseline condition.

Hematologic toxicities:

Toxicity	Action
Within-Cycle (day 8 and 15) Dose Modifications 
 • If platelet count $< 30 \times 10^9/\text{L}$ or ANC $< 0.50 \times 10^9/\text{L}$ on treatment days 8 and 15 (for dose adjustments on day 1, see below). 	
 • Hold treatment • Obtain CBC with diff 2x/week until platelet count or ANC have reached goal outlined above • Upon recovery, reinitiate treatment at 1 dose level reduction as per section 6.3.
Dose Modifications for Subsequent Treatment Cycles 
 • ANC $< 1.0 \times 10^9/\text{L}$, platelet count $< 75 \times 10^9/\text{L}$ on day 1 of a cycle. 	
 • Hold romidepsin and ixazomib until resolution as per criteria above • Obtain CBC with diff 2x/week until platelet count or ANC have reached goal outlined above • Upon recovery, reinitiate treatment at 1 dose level reduction as per section 6.3. • The maximum delay before treatment may be discontinued is 21 days and at the discretion of the local PI.

 • Delay of > 2 weeks in the start of a subsequent cycle due inadequate recovery to goals outlined above. 	
 • Hold romidepsin and ixazomib until resolution as per criteria above • Obtain CBC with diff 2x/week until platelet count or ANC have reached goal outlined above

Toxicity	Action
	
 Upon recovery, reinitiate treatment at 1 dose level reduction as per section 6.3. The maximum delay before treatment may be discontinued is 21 days and at the discretion of the local PI.

 Grade 4 febrile neutropenia or thrombocytopenia 	
 Hold treatment Obtain CBC with diff 2x/week until platelet count or ANC have reached goal outlined above Upon recovery, reinitiate treatment at 1 dose level reduction as per section 6.3.

Non-Hematological Toxicity Dose Reductions Related to Study Drugs (except alopecia)

NCI CTCAE Grade	Romidepsin	Ixazomib
0-1	No change	No change
2-3	Hold until resolved to \leq Grade 1, then resume at same level	Hold until resolved to \leq Grade 1, then resume at same level with exceptions as outlined in table “Non-hematological Toxicity Dose Reductions specific to Ixazomib”
Second episode of grade 3 OR First episode 4 toxicity	Hold until resolved to \leq Grade 1, then resume at 1 dose level reduction as per section 6.3.	Hold until resolved to \leq Grade 1, then resume at 1 dose level reduction as per section 6.3.
Third episode of grade 3 OR Second episode 4 toxicity	Hold until resolved to \leq Grade 1, then resume at 1 dose level reduction as per section 6.3. If toxicity occurs at lowest dose level, then treatment should be discontinued	Hold until resolved to \leq Grade 1, then resume at 1 dose level reduction as per section 6.3 or discontinue based on local PI judgement If toxicity occurs at lowest dose level, then treatment should be discontinued

Non-hematological Toxicity Dose Reductions specific to Ixazomib:

Peripheral Neuropathy	

 New or worsening Grade 1 peripheral neuropathy with pain or Grade 2 	
 Hold study drug until resolution to Grade \leq 1 or baseline

 New or worsening Grade 2 peripheral neuropathy with pain or Grade 3 	
 Hold study drug until resolution to Grade \leq 1 or baseline Reduce study drug to next lower dose upon recovery

 New or worsening Grade 4 peripheral neuropathy 	
 Discontinue study drug
Rash	

 Grade 2 	
 Symptomatic recommendations outlined in Section 5.4

Dosage in Patients with Hepatic Impairment

Reduce the starting dose of ixazomib to 3 mg in patients with moderate (total bilirubin greater than 1.5-3 x ULN) or severe (total bilirubin greater than 3 x ULN) hepatic impairment.

Dosage in Patients with Renal Impairment

Reduce the starting dose of ixazomib to 3 mg in patients with severe renal impairment (creatinine clearance less than 30 mL/min) or end-stage renal disease (ESRD) requiring dialysis. Ixazomib is not dialyzable and therefore can be administered without regard to the timing of dialysis.

